### **6.2. Clinical Secondary Endpoint**

- All kinds of adverse events related to surgery within 30 days
- Infarctions on the contralateral side within 1 year of randomization
- Transient ischemic attack on the surgically treated side within 1 year of randomization

- The changes from baseline in CBF measured by ASL at 7 days, 3 months, 6 months, 12 months or end of trial
- The changes from baseline in modified Rankin Scale (mRS) at 7 days, 3 months, 6 months, 12 months or end of trial
- The changes from baseline in National Institute of Health Stroke Scale (NIHSS) at 7 days, 3 months, 6 months, 12 months end of trial
- The changes from baseline in modified Barthel Scale at 7 days, 3 months, 6 months, 12 months or end of trial

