## **7. Patient Selection Criteria**

### **7.1. Inclusion criteria**

- Independent in activity of daily living(The modified Rankin Scale 0-2)
- At least one month since the most recent ischemic stroke
- The neurological deficit must be stable for more than 6 weeks
- Digital subtraction angiography demonstrating progressive stenosis or occlusion in the terminal portion of the internal carotid artery and/or the initial portion of the anterior or middle cerebral arteries
- Digital subtraction angiography demonstrating formation of abnormal collateral networks (moyamoya vessels) at the base of the brain, mainly in the region of thalamus and basal ganglia
- Digital subtraction angiography demonstrating the vasculopathy appeared unilaterally or bilaterally
- Competent to give informed consent
- Accessible and reliable for follow-up

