### **21.1. Sample size estimates**

Because this trial is a prospective, exploratory, randomized controlled trial, there is no previous data for multimodal neuronavigation guiding precise bypass procedure, the sample size for this trial can't be calculated from the formula. Finally, 100 patients are randomized (1:1) to two groups, 50 of them will undergo direct bypass guided by multimodal neuronavigation, while others will undergo empirical direct bypass procedure.

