**modified Rankin Scale**

The modified Rankin Scale (mRS) is a scale commonly used for measuring the degree of disability or dependence in the daily activities of individuals who have suffered a stroke, and it has become the most widely used clinical outcome measure for stroke clinical trials.

Description	Score (select one)
No symptoms at all	0 
No significant disability despite symptoms; able to carry out all usual duties and activities	1 
Slight disability; unable to carry out all previous activities, but able to look after own affairs without assistance	2 
Moderate disability; requiring some help, but able to walk without assistance	3 
Moderately severe disability; unable to walk without assistance and unable to attend to own bodily needs without assistance	4 
Severe disability; bedridden, incontinent and requiring constant nursing care and attention	5 

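### The mRS secondary endpoint is defined as a change from baseline, which misorders some outcomes and cannot score death; use the mRS category at the visit, adjusted for baseline

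*Protocol*

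**What the plan says.** Protocol section 6.2 lists four secondary endpoints as differences from baseline, each assessed at several visits. For blood flow the wording is "The changes from baseline in CBF measured by ASL". For disability it is "The changes from baseline in modified Rankin Scale (mRS". The neurological deficit is covered by "The changes from baseline in National Institute of Health Stroke Scale (NIHSS", while daily living is covered by "The changes from baseline in modified Barthel Scale". The synopsis lists the same four in the same form.

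Section 7.1 restricts entry to patients who are "Independent in activity of daily living(The modified Rankin Scale 0-2", and section 7.2 excludes scores 3-5. The mRS form in the appendix ends at score 5, "Severe disability; bedridden, incontinent and requiring constant nursing care and attention", and has no score for death. Death within 30 days of surgery is part of the primary endpoint (section 6.1).

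Section 21.3 gives one model, a Cox model for the primary hypothesis. It names no test or model for the four change endpoints, adjusted or unadjusted, but it does give the secondary efficacy analysis a confirmatory role. Section 21 refers full analysis details to the SAP, which is not at hand. The visit schedule collects mRS, NIHSS, Barthel and MRI at Visit 1, and section 11 requires an ASL sequence in the MRI.

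**The concern.** How a model treats baseline is normally a matter for the SAP. What the outcome is belongs to the protocol, and here the protocol makes it a difference of two mRS scores. A SAP could add a covariate, but it would have to depart from section 6.2 to analyse the mRS distribution at follow-up.

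Subtracting ordinal scores assumes that every step is worth the same. With baseline confined to 0-2, the assumption bears on which patients are counted as having done better. Differences that matter can be tied or reversed, and the worst outcome, death, has no value at all. At stake is the interpretability of a functional outcome that section 21.3 places within the confirmatory analysis. The primary endpoint is not affected.

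For CBF, NIHSS and Barthel the question is narrower: whether the collected baseline will be used as a covariate in the between-arm comparison.

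**Working it through.** **Plan's own figure.** There is none to reproduce for these endpoints. The only planning number is the sample size, "100 patients are randomized (1:1) to two groups", and section 21.1 says that it was not obtained from a formula.

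**mRS: ordering.** Inputs: baseline b in {0, 1, 2} (section 7.1); final f in {0, ..., 5} (appendix). Change = f - b.

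1. Possible change by baseline: 0 to +5 from b = 0; -1 to +4 from b = 1; -2 to +3 from b = 2. A patient who enters at 0 cannot improve.
2. Take two patients with f1 < f2, so that patient 1 ends better. There are 15 such pairs of final scores and 3 × 3 = 9 pairs of baselines, hence 15 × 9 = 135 cell pairs.
3. Change reverses the order when b2 - b1 > f2 - f1. Since f2 - f1 is at least 1 and b2 - b1 at most 2, this needs a baseline gap of 2 and a final gap of 1: 1 × 5 = 5 pairs. Example: 0→1 scores +1, and 2→2 scores 0.
4. Change ties them when b2 - b1 = f2 - f1: gap 1 gives 2 × 5 = 10, gap 2 gives 1 × 4 = 4, total 14. Example: 0→1 and 2→3 both score +1, but only the second passes from the 0-2 range to the 3-5 range.

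These are counts of possible cells. How many patients would fall in them depends on baseline and outcome distributions that the protocol does not give.

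**mRS: death.** With a top score of 5, f is undefined for a patient who has died, so the change is undefined too.

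**CBF, NIHSS, Barthel: does the definition lose precision?** In a linear model with baseline as covariate, f - b = a + τt + βb is the same model as f = a + τt + (β + 1)b. The treatment effect τ and its standard error are identical. On one simulated data set both forms gave 0.4350 with SE 0.1612. The definition alone therefore costs nothing in a linear analysis; a loss arises only if the change is compared without the covariate.

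**Size of that conditional loss.** Let ρ be the baseline to follow-up correlation and k = baseline SD / follow-up SD. Neither is in the protocol, so both are assumed. In units of the follow-up variance:

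- unadjusted change: 1 + k² - 2ρk
- baseline-adjusted: 1 - ρ²
- difference: (k - ρ)², which is never negative and is zero when ρ = k

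| ρ | k = 1 | k = 0.5 |
|---|---|---|
| 0.3 | 1.40/0.91 = 1.54 | 0.95/0.91 = 1.04 |
| 0.5 | 1.00/0.75 = 1.33 | 0.75/0.75 = 1.00 |
| 0.7 | 0.60/0.51 = 1.18 | 0.55/0.51 = 1.08 |
| 0.9 | 0.20/0.19 = 1.05 | 0.35/0.19 = 1.84 |

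Entries are the variance of unadjusted change divided by the baseline-adjusted variance.

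**The case against.** The strongest reply is that section 6.2 names variables, not tests, and that covariates belong in the SAP. This is right for CBF, and for NIHSS and Barthel if they are analysed linearly. A reader might infer that the plan commits to raw, unadjusted change scores on all four outcomes, and so gives up a calculable amount of power and lets chance baseline imbalance into the estimates. The protocol does not support that. It states no unadjusted analysis; ρ and k are unknown; and a restricted entry range may make the baseline spread narrower than the follow-up spread, where for ρ of 0.3 to 0.7 the table shows almost no loss. Under randomisation an unadjusted comparison of changes is also unbiased on average. No power figure can be given as a property of this plan.

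On mRS, one can say that moving from 0 to 1 really is a deterioration and staying at 2 is not, so that change measures something legitimate. One can add that only 5 of 135 cell pairs are reversed, and that the 0-2 entry limit itself keeps reversals few. Both points are fair and limit the size of the problem. They do not remove the ties, the assumption of equal steps or the missing score for death. Nor does adding a covariate in the SAP settle it. The linear identity recovers the follow-up comparison only by treating the steps as equal, and it does not carry over to an ordinal model of change. A rank analysis would recover the ordering only if fully stratified by baseline, because within one baseline score change and final score rank patients alike.

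Two limits of the remedy should be conceded. A patient at 0 still cannot improve, and floor or ceiling effects on NIHSS and Barthel, plausible in independent patients but not documented, remain after adjustment. The death problem is solved by the added category, not by giving up change as such.

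**Conclusion.** The point holds for the mRS endpoint as defined. Change from baseline equates 0→1 with 2→3, ranks 0→1 below 2→2, reverses 5 and ties 14 of 135 cell pairs, and gives no value to patients who die. This follows from the entry rule and the printed scale and needs no assumed figures, apart from taking the better final state as the better outcome.

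For CBF, NIHSS and Barthel there is no fault in the definition, only a useful clarification. If the SAP left out the covariate, the variance would be larger by a factor of 1.18 to 1.54 with equal SDs, or 1.00 to 1.08 with a baseline SD half the follow-up SD, for assumed ρ of 0.3 to 0.7. Outside that range of ρ the factor can be larger, as the last row of the table shows.

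These are secondary endpoints in a trial that section 21.1 calls exploratory, so the main conclusion is little affected. The change is worth making because it gives a better measure at almost no cost.

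**What to change.** In section 6.2 and the synopsis, define the mRS endpoint as the mRS category at each listed visit, with a further category for patients who have died by then. State that the arms are compared by a proportional-odds model with baseline mRS as covariate, and report change from baseline as a descriptive column only.

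For CBF, NIHSS and Barthel, keep the change definition if preferred and add that the Visit 1 value is a covariate in the between-arm comparison. Bring the SAP into line.

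The cost is wording in two protocol sections and the SAP. The baseline values are already scheduled at Visit 1, so no visit, assessment or patient is added.

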## **7. Patient Selection Criteria**

### **7.1. Inclusion criteria**

- Independent in activity of daily living(The modified Rankin Scale 0-2)
- At least one month since the most recent ischemic stroke
- The neurological deficit must be stable for more than 6 weeks
- Digital subtraction angiography demonstrating progressive stenosis or occlusion in the terminal portion of the internal carotid artery and/or the initial portion of the anterior or middle cerebral arteries
- Digital subtraction angiography demonstrating formation of abnormal collateral networks (moyamoya vessels) at the base of the brain, mainly in the region of thalamus and basal ganglia
- Digital subtraction angiography demonstrating the vasculopathy appeared unilaterally or bilaterally
- Competent to give informed consent
- Accessible and reliable for follow-up

### **7.2. Exclusion Criteria**

- Other diseases(such as internal carotid artery stenosis, internal carotid artery dissection, atrial fibrillation, or Intracranial atherosclerosis) probably causing ischemic strokes
- Not independent in activity of daily living(The modified Rankin Scale 3-5)
- Moyamoya syndrome concomitant with other hereditary or autoimmune diseases (Grave's Disease, Type I Diabetes Mellitus, Type I Neurofibromatosis et al)
- Patient whose initial onset was marked by ischemia but subsequently suffered from intracranial hemorrhage
- Emergent evacuation of intracerebral hematoma damaging superficial temporal artery or cortical artery
- Emergent decompressive craniotomy causing automatically developed indirect revascularization
- Good collateral networks formed by spontaneous anastomosis between

extracranial and intracranial vessels before surgery

- Life expectancy < 1 years
- Pregnancy
- Unstable angina or myocardial infarction with recent 6 months
- Blood coagulation dysfunction
- Allergic to iodine contrast agent
- Abnormal liver function (alanine transaminase (ALT) and/or aspartate aminotransferase (AST) > 3 times of normal range)
- Serum creatinine > 3mg/dl
- Poorly controlled hypertension (systolic BP > 160 mmHg, diastolic BP > 100 mmHg)
- Poor glucose control (fasting blood glucose > 16.7 mmol/l)
- Concurrent participation in any other interventional clinical trial
- patients refused to participate in the study

## **8. Informed Consent**

The principles of Informed Consent, according to FDA Regulations and ICH guidelines on GCP, will be followed. Investigator will submit a copy of the proposed consent form, together with the study protocol, to the central Institutional Review Board (IRB) at Peking University International Hospital for approval. Each eligible patient who wishes to participate in this study will be invited to give written informed consent. Before the consent is signed, a trained researcher will explain study purpose, description, duration, potential risks and anticipated benefits, cost and compensation, voluntary nature of participation, appropriate alternatives, treatment for study-related injury, whom to contact with questions or concerns or study-related injuries, maintenance of confidentiality of record, and funding source. Patients will be encouraged to consent for the blood drawing for biomarker testing only if they would be prepared to enroll in the trial.

## **9. Enrollment of Patients**

All of Patients who meet the clinical criteria will undergo MRI, CTP and DSA. Patients with progressive stenosis or occlusion in the terminal portion of the internal carotid artery and/or the initial portion of the anterior or middle cerebral arteries unilaterally or bilaterally and formation of abnormal collateral networks (moyamoya vessels) at the base of the brain according to DSA, hypoperfusion based on perfusion CT or DSA and no significant new infarction lesions on MRI will be asked to participate and sign consent. Once this is completed, the patient will be enrolled and, if randomized to multimodal neuronavigation guiding precise bypass group, will undergo multimodal neuronavigation guiding precise bypass surgery after enrollment.

## 10. Randomization of Patients

The central randomized method based on our own system. Patient who has signed the informed consent form and met all inclusion criteria without any exclusion item could be enrolled. Once the patient enrolled in the study, the system will automatically assign the study patient a random number with the exact group that he/she should be treated. Then the investigator should record this number and group in the original case history and the coming treatment record of the study patient. According to the protocol, this patient should be treated into the randomized group or the control group.

The investigator's team should archive the randomized list and the related documents (randomized application form) together in the trial folder, which clinical trial department of the site has to store.

## 11. Image Data Evaluation

Considering the quality of the angiographic images in the trial, we will select participating sites which are available to have access to state-of-the-art cerebral angiography facilities. The investigators in each site will be trained and certificated for image acquisition and measurement before the startup phase of the trial.

The angiographic imaging showed internal carotid artery stenosis/occlusion site, moyamoya vessels and vascular compensatory level. MRI should contain structure sequence and ASL sequence.

When a patient is enrolled in the trial, core lab will obtain CD copies of angiographic images, CT perfusion and MRI for central review. Images of the cerebral artery, CT perfusion and MRI post revascularization surgery also must be sent to core lab for central review.

## 12. Multimodal Neuronavigation Procedure

**Pre-procedure:** All patients randomly assigned to both arms will be suspend aspirin 7 days before the revascularization procedure and restart taking aspirin on the first day postoperatively.

**Intra-procedure:** The surgical procedure will be done under the general anesthesia. ICG fluorescence angiography using Flow800 software and electromagnetic neuronavigation system is required during the procedure of revascularization. An

initial ICG fluorescence angiography will be performed when the dural membrane is unfolded to expose the blood vessels on the surface of the brain. According to the appearance order of vessels to assess the velocity of cerebral flow. Neuronavigation system is used to judge the cerebral hypoperfusion area under different recipient vessels. The vessel was chosen as the receptor with lower flow velocity and lower cerebral perfusion area to perform anastomosis.

Papaverine is used to prevent the occurrence of vasospasm. During surgery, the heparinized water was used to flush the donor's and the receptor's lumen for minimization of thrombosis or thromboembolism risk. An anastomotic end-to-side continuous (or intermittent) suture was performed using a 10-0 nonabsorbable vascular suture thread.

**Post-procedure:** Aspirin 100mg per day must be used for the entire duration of follow-up. Clopidogrel is not necessary after the surgery unless a cardiologist recommends taking clopidogrel for a cardiac indication.

### **13. Antithrombotic therapy**

All participants will take aspirin 100 mg per day for entire follow-up after the revascularization surgery. Suspend aspirin 7 days before surgery, if necessary (Previous vascular stent implantation history), replace the treatment with low molecular weight heparin. If patients have been prescribed long-term use of clopidogrel for indications of coronary disease or peripheral vascular disease, taking clopidogrel at the same time..

### **14. Management of Risk Factor**

#### **14.1. Primary Risk Factors**

##### **Blood Pressure Control**

Measurement and treatment of blood pressure (BP) in this study will be based on JNC 7 guidelines. The trained study coordinators at each participating site perform blood pressure measurement using standardized blood pressure monitors. Blood pressure will be measured at randomization, at discharge, at 3 months, at 6 months, and at the end of trial. Some patients would be required to come back to clinic for checking blood pressure and to modify regimen of blood pressure management. Given a likelihood of impaired cerebral perfusion resulting subsequent stroke, blood pressure of 130-140/90-95 mmHg will be maintained regardless of whether patients have diabetes or not. Patients will be considered "in target" when the blood pressure at one visit is under ranges of 130-140/90-95 mmHg.

Antihypertensive drug (Angiotensin-converting enzyme [ACE] inhibitor, Angiotensin Receptor Blocker [ARB], beta-blocker, calcium channel antagonist, diuretic, vasodilator, etc.) will be not free of charge to study patients. Drugs can be chased from each participating site for use by study patients.

As part of routine care, serum creatinine will be checked at baseline, at 3 months, at 6 months, and at the end of trial. It will be anticipated that a repeating test of serum creatinine during a period of follow-up might be required one month after changing dose of an ACE inhibitor or for assessing whether renal function is impaired or not. Additionally, all patients will have a potassium level checked at randomization, one month after changing the dose of a diuretic or ACE inhibitor, at 3 months, and 6 months after study entry.

#### **14.2. Secondary Risk Factors**

##### **Non-HDL Cholesterol**

Non-HDL cholesterol <100 mg/dL is considered an important secondary target. Non-HDL cholesterol contains LDL, very low density lipoproteins (VLDL) and intermediate density lipoproteins (IDL). Once the dose of statin has been not increased to lower LDL, if non-HDL cholesterol  $\geq$  100 mg/dL and triglycerides  $\geq$  200mg/dL, fenofibrate (Tricor) 145 per day will be recommended to patients.

##### **Treatment for Diabetes**

HgA1c < 7.0% will be the target of diabetes management according to recommendations of the American Diabetes Association (ADA). HgA1c testing should be performed at baseline, at 3 months, and at 6 months to ensure glycemic goals to be met. Other items about management of diabetes are based on Recommendations from ADA Position Statement for Standard of Medical Care in Diabetes (ADA, 2006). Achieving good diabetic control might need a cooperation of a multidiscipline team including patients, study neurologists, primary physicians, and even endocrinologists.

##### **Smoking Cessation**

Study investigators at each site will assess current smoking status and cigarette quantity per day at every study visit. Every study patient will be educated or encouraged to quit smoking at study entry and during follow-up, as appropriate.

##### **Management of Body Weight**

Weight will be assessed at each follow-up visit and body mass index (BMI) calculated by dividing measured weight in kilograms by the square of measured height in meters. Targeted goals of BMI management depend on the initial BMI: the target BMI is < 25 kg/m^2 if the initial BMI is 25-27 kg/m^2; a 10% weight reduction will be targeted if the initial BMI >27 kg/m^2. Details for weight management are based on 2013 AHA/ACC/TOS Guidelines for Treatment of Overweight and Obesity in Adults.

## **Medications**

ASA counts will be done for assessment of patient compliance at every study visit.

Atorvastatin will be given to study patients with LDL > 70 mg/dL. If other lipid-lowering drug is taken, patients will be encouraged to switch to atorvastatin. But, it is not mandatory.

Study patients not achieving the target of blood pressure will be prescribed antihypertensive drugs. Patients can choose but not limited to the following drugs for antihypertension:

- ✧ A diuretic (chlorthalidone 25 mg)
- ✧ an ACE inhibitor (lisinopril 10 and 40 mg)
- ✧ an angiotensin receptor blocker (candesartan (Atacand) 16 and 32 mg)
- ✧ a beta-blocker (atenolol 50 and 100 mg)
- ✧ a vasodilator (hydralazine 50 mg)
- ✧ a central alpha agonist (clonidine 0.1 mg)
- ✧ a long-acting calcium channel antagonist (felodipine 5 and 10 mg)

## **Exercise**

Physical activity status will be assessed at each study visit by study trained investigators or coordinators according to Guide to the Assessment of Physical Activity of the American Heart Association (Clinical and Research Applications). Physical activity will be strongly encouraged to all enrolled patients. Moderate intensity activities will be recommended at least 3 times per week for 30 minutes per session if patients have ability to do it.

